529 670G pump to a research Carelink account every 2 weeks. Their data will be
530 reviewed within 3 days by the clinicians managing the study at each research
531 clinical site. An email, text or phone call will be made to the subject after reviewing
532 their pump/sensor data. Recommendations for dosage changes will be recorded on
533 a case report form or directly into RedCap. The study investigators will meet every
534 2 to 4 weeks during the study to review clinical issues and insights that have been
535 observed.

536

537 To assess the long term effect of using Fiasp® on infusion sites and insulin action,
538 they will be asked to use Fiasp® as long as they see benefit in using it after the
539 initial meal boluses testing is completed. Each time they change their infusion set,
540 we will ask them to examine the site for any bleeding, redness or induration, and
541 measure these changes and take a picture if there are any findings. (See
542 Documentation of infusion site reactions). We will have them download to a
543 CareLink research data base every two weeks to look at their total daily insulin
544 requirements, glucose values, and basal insulin requirements with extended use of
545 Fiasp®. They will have an email sent to them every 2 weeks by RedCap to assess
546 for issues they have observed while using Fiasp®.

547

548 *Documentation of infusion site reactions:* At home subjects will exam their infusion
549 set site when they are changing an infusion set and assess for bleeding, signs of a
550 local tissue reaction or infection. They will record redness, induration, and bruising
551 in mm, and call one of the investigators if there is more than 10 mm of erythema or
552 induration. They will be given a ruler for making these measurements. If there is
553 more than 3 mm of induration or redness they will be asked to take a picture and
554 enter these measurements and send a text to the study coordinator or submit the
555 information directly into RedCap.

556

557 They will be instructed to replace the infusion set if:

- 558 1. Their ketone level is greater than 0.6 mmol/L,
- 559 2. There is evidence of infection at the infusion site
- 560 3. Their blood glucose (meter) does not decrease by at least 50 mg/dL within 1
561 hour of a correction bolus for unexplained hyperglycemia with a blood
562 glucose greater than 250 mg/dL.
- 563 4. There is a pump occlusion alarm.

564

565 **CHAPTER 4: ADVERSE EVENT REPORTING AND PROTOCOL MONITORING**

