772 the time of the bolus. The glucose at the time of the breakfast bolus (Time 0) will be
773 set to 0 mg/dL for each meal, and the remaining CGM values were adjusted
774 proportionally to allow analysis of postprandial glucodynamic parameters. We will
775 utilize a mixed-effects model accounting for crossover study design of the study with
776 the sequence of treatment nested within the patient. Breakfast meals are excluded
777 from postprandial analysis if: 1) the rate of change was greater than 0.3mg/dL/min
778 in the 1 hour prior to breakfast, 2) subjects gave a subsequent bolus prior to 120
779 minutes following the breakfast bolus, or 3) subjects deviated from their typical
780 breakfast. Dinner meals will be assessed when there has been no additional food
781 intake after dinner. The duration of insulin delivery to cover the meal will be
782 determined by the time it takes the post prandial glucose to reach 160 mg/dL
783 beyond 1 hour of eating. The peak glucose will also be recorded.

783

784 During the 6 week optimization study (Part II) we will use data obtained during the
785 first two weeks of the study (before data was reviewed and changes made by the
786 investigators) to data obtained during the last two weeks of the 3 month optimization
787 period. We will compare the following measurements using paired t-tests for data
788 with a normal distribution and a Mann-Whitney rank sum test for data that is not
789 normally distributed:

790

a) time in range (70-180 mg/dl)

791

b) percent time <70 mg/dl,

792

c) mean glucose,

- 793 d) glucose CV,
- 794 e) total daily insulin dose,
- 795 f) total daily basal insulin,
- 796 g) insulin delivery form MN to 6AM, and 6AM to MN
- 797 h) CHO:I ratios at breakfast, lunch and dinner
- 798 i) Active insulin time
- 799 j) Number of days between infusion set changes
- 800 k) Erythema (mm) and induration (mm) at infusion sites when they are changed
- 801 l) Average daily insulin, and mean glucose for each day of infusion set wear
- 802 m) Number of episodes of unexplained hyperglycemia in the first month vrs the
- 803 last month
- 804
- 805
- 806
- 807

808 **CHAPTER 7: REFERENCES**

809

- 810 1. Heise T, Hovellmann U, Nosek L, Sassenfeld B, Thomsen KMD, Haahr H.
811 Pharmacokinetic Properties of Fast-acting Insulin Aspart Administered in Different
812 Subcutaneous Injection Regions: Response to the commentary by Nuggehally R. Srinivas.
813 Clinical drug investigation 2017.

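### Part 2 compares two periods in the same subjects, but sends non-normal endpoints to the Mann-Whitney test, which assumes independent groups

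*Combined protocol and SAP*

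**What the plan says.** The Part II paragraph of Chapter 6 (Statistical Considerations) sets data from the "first two weeks of the study (before data was reviewed and changes made by the" investigators against data from the end of the period: "investigators) to data obtained during the last two weeks of the 3 month optimization" period. Both sets come from the same people. Chapter 2 (Study Enrollment and Duration) describes Part 2 as a single group of up to 20 Fiasp users, with no comparison arm.

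The tests are named in one sentence. It begins "period. We will compare the following measurements using paired t-tests for data" and continues "with a normal distribution and a Mann-Whitney rank sum test for data that is not" normal. Thirteen items, a to m, follow. Three of them matter particularly here:

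- Item j: "Number of days between infusion set changes".
- Item k: "Erythema (mm) and induration (mm) at infusion sites when they are changed". Chapter 3, Part 2 has subjects inspect the site "Each time they change their infusion set", so one subject contributes several records per period.
- Item m: "Number of episodes of unexplained hyperglycemia in the first month vrs the" last month. This item uses months rather than two-week windows.

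The plan does not say whether normality is judged on each period's values or on the within-subject differences. It gives no per-subject summary for items j and k. The mixed-effects models in Chapter 6 are for Part 1 only.

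**The concern.** The paired t-test shows that the authors regard the two periods as paired. The rank test in the same sentence drops the pairing. Mann-Whitney computes its null variance as if the 40 values came from 40 unrelated people.

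The direction of the error depends on how the data enter the test:

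- **One value per subject per period, positively correlated.** The assumed variance is too large, the test is conservative, and real changes are more likely to be missed. Chapter 6 says the study is meant to find clinical issues with Fiasp in the 670G, so a missed change could be read as no issue.
- **Several records per subject pooled as if independent (items j and k).** The assumed variance can be too small, so changes in set life or site reactions could appear by chance too often.

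The plausible candidates for the rank test are percent time <70 mg/dL, days between set changes, erythema and induration, and hyperglycemia counts.

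**Working it through.** The plan states no power, alpha or effect size for Part 2, so there is no figure of its own to reproduce. The mismatch itself follows from the text; the calculations below only show its size.

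**Inputs.** From the documents: 20 subjects (the planned maximum), and 3.3 ± 2.0 for percent time <70 mg/dL on the 670G (Table 1, section 1.2.2). Assumed: two-sided 5%, within-subject correlation ρ from 0 to 0.8, a 0.5 SD shift or a 30% fall, and the variance shares in step 3. Each setting has 10,000 simulated trials.

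**1. One value per subject per period, normal data.**

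| ρ | Mann-Whitney type I error | Mann-Whitney power | Signed-rank power |
|---|---|---|---|
| 0 | 5.1% | 31.7% | 30.6% |
| 0.1 | 4.1% | 31.4% | 33.8% |
| 0.3 | 2.1% | 29.1% | 41.0% |
| 0.5 | 0.8% | 27.2% | 54.6% |
| 0.7 | 0.2% | 23.9% | 75.4% |
| 0.8 | 0.0% | 21.6% | 90.3% |

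Signed-rank type I error is 4.6–5.2% throughout.

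Analytic check: pairing multiplies the true variance of the rank-sum statistic by about 1 − ρs, where ρs = (6/π)·arcsin(ρ/2). The type I error is then about 2·[1 − Φ(1.96/√(1 − ρs))]. For ρ = 0.5, ρs = 0.483, √0.517 = 0.719 and 1.96/0.719 = 2.73, giving 0.6% (simulated 0.8%). For ρ = 0.3 the formula gives 2.0% (simulated 2.1%).

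**2. A skewed endpoint.** For 3.3 ± 2.0, a normal curve puts Φ(−3.3/2.0) = Φ(−1.65) = 4.9% below zero, which is modest evidence of skew. A log-normal with that mean and SD has log-SD = √ln(1 + (2.0/3.3)²) = 0.56. With a 30% fall and ρ on the log scale:

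| ρ | 0 | 0.1 | 0.3 | 0.5 | 0.7 | 0.8 |
|---|---|---|---|---|---|---|
| Mann-Whitney power | 47.6% | 48.1% | 47.7% | 47.9% | 48.3% | 49.1% |
| Signed-rank power | 44.0% | 48.1% | 57.5% | 72.8% | 89.9% | 97.7% |

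**3. Items j and k, if records are pooled.** Let total variance be 1, with between-subject share b, subject-by-period share s and residual 1 − b − s, and m records per subject per period. The true variance of the difference in means, relative to what an independent-groups test assumes, is m·s + (1 − b − s) = 1 − b + (m − 1)s. The test is therefore conservative while (m − 1)s < b and anti-conservative once (m − 1)s > b. With b = 0.3, simulated Mann-Whitney type I error is:

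| Records per period | s = 0 | 0.05 | 0.1 | 0.2 | 0.3 |
|---|---|---|---|---|---|
| 3 | 2.2% | 3.0% | 4.4% | 6.3% | 9.3% |
| 5 | 2.2% | 4.4% | 6.4% | 11.3% | 15.8% |
| 7 | 2.2% | 5.4% | 8.4% | 15.5% | 21.7% |

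These counts correspond to roughly one set change every 5, 3 or 2 days over 14 days. For m = 5 and s = 0.1 the ratio is 0.7 + 0.4 = 1.1, and 2·[1 − Φ(1.96/√1.1)] = 6.2%, close to the simulated 6.4%. One mean per subject per period with the signed-rank test gives 4.6–5.2%.

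**4. How often the rank test would be reached.** The plan names no normality test. As an illustration, Shapiro-Wilk at 5% on samples of 20 from the step 2 scenario (3,000 trials) rejects about 60% of single-period samples. On the differences it rejects 26–44% across ρ 0 to 0.8; the upper end depends on the assumed 30% fall (24–31% with no change, 5,000 trials).

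**The case against.** The strongest objection concerns the false-positive direction. The same sentence prescribes paired t-tests for the whole list, and a paired t-test needs one value per subject per period, so pooling raw records is the less natural reading. This stands. The plan leaves a gap rather than calling for pooling, and even pooled records inflate the error only when the subject-by-period share is large enough. Loss of power is the better-supported consequence; inflation remains conditional.

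Second, little in the documents shows how many endpoints would reach the rank test. The one usable figure, 3.3 ± 2.0, is a 3-month value from a trial in which 30 of 124 subjects were aged 14–21, whereas this study requires age 18 or over. The log-normal shape is assumed. This also stands: the number of affected endpoints is unknown.

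Third, Part 2 is an unpowered pilot with no stated alpha or decision rule, and the analysis can be corrected on the same data. That limits the consequence but does not make the test right. A small study can least afford to discard its pairing.

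If Mann-Whitney is simply a slip for the Wilcoxon signed-rank test, the correction is trivial. An analyst following the text would still run the wrong test.

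**Conclusion.** The concern holds: the non-normal branch of the Part 2 analysis is wrong as written, whatever the correlation. The size of the effect depends on quantities the plan does not give. With one value per subject per period, the loss is negligible at correlations of 0 to 0.1. At 0.5, power for a 0.5 SD shift is halved (27.2% against 54.6%), and the gap widens beyond that. Under pooling of items j and k, type I error ranges from 2.2% to 21.7% over the assumed settings with b = 0.3. This should be fixed before analysis, but no confirmatory conclusion depends on it.

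**What to change.** Change the Part II paragraph of Chapter 6 as follows:

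- Replace the Mann-Whitney rank sum test with the Wilcoxon signed-rank test on within-subject differences, and state how zero differences are handled, since site findings may produce many.
- Judge normality on the within-subject differences. Fewer endpoints would then reach the rank test, though not none.
- Before testing, reduce items j to l to one summary per subject per period (for item l, per day of set wear).
- Pair item m within subject and use windows that do not overlap. If Part 2 lasts 6 weeks, two 28-day months share 2 × 28 − 42 = 14 days.
- State that a subject without a second, non-overlapping period cannot enter the paired test. Report how many there are and keep their data in descriptive summaries, consistent with Chapter 5 on using data up to withdrawal. Chapter 2 lets subjects stop early, so this can arise.

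Separately, the 6-week and 3-month descriptions of Part 2 (Chapter 6, and the HbA1c section of Chapter 2) must be reconciled, because they determine when the late period falls. Either duration leaves the comparison paired.

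The cost is a few sentences of analysis wording, with no new data and no change to study conduct.

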243 optimization phase to assess if making changes to meal coverage with the
244 knowledge that Fiasp® is being used can optimize the advantages of the 670G
245 pump with Fiasp® use, and to observe longer term use of Fiasp® in the 670G
246 pump. This will be a 6 week study.

247

248 *Part 1: Randomized cross-over, blinded study which includes assessment of meal*
249 *pharmacodynamics.*

250 Part 1 will be a randomized cross-over blinded study and will also test to see how
251 the 670G pump responds to the introduction of Fiasp® insulin. Subjects enrolled in

252 the study will have a 2 week period of optimization with weekly assessments of their
253 Carelink download before entering the blinded phase of the study. They will use
254 their usual home insulin during the optimization phase. They will then be started
255 on their first blinded insulin (aspart or Fiasp®) which they will use for 2 weeks,
256 before they cross-over to the other insulin. During the second week of each arm we
257 will:

- 258 1) Assess CGM measurements of:
 - 259 a) time in range (70-180 mg/dl)
 - 260 b) percent time <70 mg/dl,
 - 261 c) mean glucose,
 - 262 d) glucose CV,
- 263 2) Pump data for:
 - 264 a) CHO:I ratios at Breakfast, Lunch and Dinner,
 - 265 b) total daily insulin dose,
 - 266 c) total daily basal insulin,
 - 267 d) insulin delivery from MN to 6AM, and 6AM to MN
- 268 3) We will test to see if there is any difference in pharmacodynamics when
269 using Fiasp® in the home environment when they are eating their usual
270 breakfast.
- 271 4) We will also assess their glucose levels following a high fat meal at dinner of
272 at least 30 grams of fat.

273

274 *Part II: Extended Use Observational Study.*

275 This study will consist of 6 weeks of closely monitored home use of the 670G pump
276 with review of their pump and sensor downloads every 2 weeks by clinicians who
277 are experienced in using the 670G pump. The goals of this phase of the study are
278 to:

- 279 1) Assess how Fiasp® changes meal bolusing, i.e. do adjustments need to be
280 made in their carbohydrate to insulin ratios or timing of their boluses when
281 they are using Fiasp® I
- 282 2) Assess how Fiasp® works with the higher fat meals that may occur with
283 dinner, i.e. will the dinner dose need to be divided into early and late boluses
- 284 3) Assess how Fiasp® affects infusion sites under usual care conditions, i.e are
285 there any local reactions to Fiasp®

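### Part 2 asks whether local reactions occur during Fiasp use, but item k tests only whether redness and induration change between two on-Fiasp windows; the frequency of reactions should be the main analysis.

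*Combined protocol and SAP*

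**What the plan says.** The Protocol Synopsis (section 1.4, Part II, goal 3) sets the question: "Assess how Fiasp® affects infusion sites under usual care conditions, i.e are" "there any local reactions to Fiasp".

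Chapter 3, Part 2, has subjects examine the site at each set change and record redness, induration and bruising "in mm, and call one of the investigators if there is more than 10 mm of erythema or" induration. Above 3 mm of redness or induration they take a picture and send in the measurements.

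Chapter 6 gives one rule for all Part II measurements. It sets data from the "first two weeks of the study (before data was reviewed and changes made by the" "investigators) to data obtained during the last two weeks of the 3 month optimization" period. The tests are stated as follows: "period. We will compare the following measurements using paired t-tests for data" "with a normal distribution and a Mann-Whitney rank sum test for data that is not" normally distributed. Item k, "Erythema (mm) and induration (mm) at infusion sites when they are changed", falls under that rule. Chapter 6 names no proportion of sites or subjects with a reaction, no size limit, no confidence interval and no descriptive summary for site findings. The Part I list has no site item.

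Eligibility criterion 14 and the Part 2 procedures both require that Part 2 subjects already use Fiasp as usual care.

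**The concern.** Goal 3 asks whether reactions happen and, by extension, how often. Item k asks whether their size in millimetres differs between early and late use. These are different quantities. An early-versus-late contrast suits pump settings, which investigators change after the first window. It does not suit skin findings, because the first window is not a Fiasp-free baseline.

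Three consequences follow if Chapter 6 is applied as written:

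- A steady reaction rate produces no expected difference, however high it is.
- Set changes between the two windows do not contribute.
- Participation runs for up to 6 weeks or until the subject chooses to stop Fiasp. Someone who stops early, perhaps because of site reactions, may have no separate late window and so drop out of a paired comparison. The withdrawal rules keep data up to withdrawal, but a paired test needs both windows.

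**Working it through.** The plan states no power, alpha or precision figure for site findings, so there is none to reproduce.

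**1. What item k estimates.** For a subject with constant per-site reaction probability p and mean reaction size m, mean mm per site is p × m in both windows. The expected difference is p × m − p × m = 0 for every p.

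**2. Simulation of item k.** All settings are assumptions: 20 subjects, 4 or 7 set changes per window, p constant over time at 5%, 10%, 25%, 50% or 80% on average, subject-to-subject variation Beta with total 4, reactions uniform on 3 to 10 mm, clean sites 0 mm, two-sided alpha 0.05, 4,000 runs per setting. The paired t-test rejected in 2.2% to 5.5% of runs. The Mann-Whitney test, which ignores the pairing, rejected in 0.3% to 1.6%. In practice a steady 80% rate is flagged no more often than a false positive would be.

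**3. Available set changes.** Inputs: up to 20 subjects and 6 weeks (42 days), both from Chapter 2; 3-day wear is assumed.

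- 20 × 42 / 3 = 280, or 14 per subject.
- With 4-day wear, 20 × 42 / 4 = 210; with 2-day wear, 20 × 42 / 2 = 420.
- These are ceilings, because enrolment and duration are both stated as upper limits.

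**4. Share unused by item k.** The two windows cover 28 days.

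- On 42 days: 1 − 28/42 = 33%.
- On 3 months, taken as 91 days: 1 − 28/91 = 69%.
- Chapter 6 uses both durations in the same sentence, so the share cannot be fixed until they are reconciled.

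**5. Precision of a per-site proportion.** Assume a 10% rate and 280 set changes.

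- No clustering: 1.96 × √(0.1 × 0.9 / 280) = ±3.5 points.
- Design effect 2, which implies an intraclass correlation of (2 − 1)/(14 − 1) = 0.08: 3.5 × √2 = ±5.0 points.
- The heterogeneity used in step 2 has intraclass correlation 1/(4 + 1) = 0.2. The design effect is 1 + 13 × 0.2 = 3.6, giving 3.5 × √3.6, about ±6.7 points.

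**6. Precision of a per-subject proportion.** Two-sided exact 95% intervals for 20 subjects:

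| Subjects affected | 95% CI |
|---|---|
| 0/20 | 0 to 16.8% |
| 1/20 | 0.1 to 24.9% |
| 2/20 | 1.2 to 31.7% |
| 5/20 | 8.7 to 49.1% |

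The upper limit for 0/20 is 1 − 0.025^(1/20) = 16.8%. The one-sided version, 1 − 0.05^(1/20) = 13.9%, should not be mixed with two-sided intervals. The chance of seeing at least one affected subject is 1 − (1 − π)^20: 64%, 88% and 99% for true subject rates π of 5%, 10% and 20%.

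**The case against.** **Levels would be visible.** Comparing millimetres in two windows means computing the level in each, so a steady high rate would appear as two high values with no difference. This stands, and it limits the claim. A reader might infer that Part 2 is bound to report nothing or leave its safety question unanswered. The documents do not support that: larger reactions prompt a picture or a call, subjects are asked about issues every two weeks, and investigators meet every 2 to 4 weeks. None of these is a specified analysis of goal 3, however. Adverse-event reporting does not supply one either. It covers events that are serious, or unexpected and related, while local tissue reactions are a listed risk.

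**A proportion cannot attribute reactions to Fiasp.** This also stands. Part 2 has no aspart arm, the protocol itself names adhesive reactions as a risk, and people who reacted badly may have stopped Fiasp before entry. It would be wrong to infer that incidence answers the causal part of goal 3 without a comparator.

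**The denominator is not secured.** Subjects measure and photograph findings, but nothing says that a clean site generates a record. A set change with no report could be a clean site or an uninspected one. This stands, so the change needs a recording rule as well as an analysis sentence.

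**The study is an unpowered pilot.** True, but that favours a descriptive estimate with an interval over an unpowered test of change.

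**Conclusion.** The mismatch between goal 3 and item k is real. The first-versus-last contrast has expectation zero under any constant reaction rate and cannot, as a test, say whether or how often reactions occur. That conclusion follows from the text and does not depend on the simulation settings.

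The size of the gain rests on assumptions: 3-day wear, full enrolment of 20, 42 days for everyone and a 10% site rate. Under these, at most about 280 set changes would give roughly ±3.5 points ignoring clustering, and ±5 to ±7 with design effects of 2 to 3.6. The share of follow-up that item k leaves unused is one third on 42 days and about 69% on 91 days; neither can be stated as the plan's figure yet.

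The gap is in the analysis and recording rules. It does not show that reactions would go unnoticed, and closing it would not show that Fiasp caused them.

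**What to change.** In Chapter 6, make the main analysis for goal 3:

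- the proportion of all Part 2 set changes with redness or induration above 3 mm, and above 10 mm, each with a 95% confidence interval that allows for clustering by subject;
- the proportion of subjects with at least one such site, with a two-sided exact 95% interval.

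Keep the early-versus-late comparison in item k as a secondary look at change over time.

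Define the denominator: count set changes from the pump downloads, record an inspected clean site as 0 mm, and treat an uninspected site as missing. Report the number missing.

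State that, with no aspart comparator and only current Fiasp users enrolled, the result describes site reactions during Fiasp use and does not attribute them to Fiasp. Reconcile the 6-week and 3-month wording so that the follow-up period is defined.

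The cost is a few sentences in Chapter 6 and a short entry per set change for clean sites. Site examination at each change and regular pump downloads are already planned, so no visits are added.

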- 286 4) Assess if Fiasp® becomes less effective over the life an infusion set (are sets
287 changed more frequently)
- 288 5) Assess how the 670G performs when Fiasp® is used:
 - 289 a. Do insulin-to-carbohydrate ratios need to be modified
 - 290 b. Does duration of insulin action need to be modified
 - 291 c. Is more or less basal insulin delivered
 - 292 d. Does the total daily dose change
 - 293 e. Does the performance of the 670G change overnight (MN to 6AM)
294 and during the day (6AM to MN) in terms of time in range, mean
295 glucose and % of readings <70 mg/dL.

296

297 will include both males and females and an enrollment goal will be to achieve an

298 approximately equal sex distribution. Their total daily insulin dose should be at least
299 0.3 units/kg/day and they should be eating at least 60 grams of carbohydrate each
300 day.

301

302 **General Considerations**

303 The study is being conducted in compliance with the policies described in the study
304 policies document, with the ethical principles that have their origin in the Declaration
305 of Helsinki, with the protocol described herein, and with the standards of Good
306 Clinical Practice.

307

308 **CHAPTER 2: SUBJECT ENROLLMENT AND STUDY INITIATION**

309

310 **Study Enrollment and Duration**

311 Part 1: Randomized cross-over, blinded study with assessment of meal
312 pharmacodynamics: up to 20 subjects will be studied and the studies for each
313 subject will last 6 weeks.

314 Part 2: Long term use of Fiasp®. We will recruit up to 20 subjects who are using
315 Fiasp® insulin, they are not excluded if they were in Part 1, in fact subjects in part 1
316 will be encouraged to continue into part 2 of the study. Duration is up to 6 weeks, or
317 until subject decides to stop using Fiasp®.

318

319 **Eligibility and Exclusion Criteria**

320

321 **Eligibility Criteria**

322 To be eligible for the study, a subject must meet the following criteria:

- 323 1. Clinical diagnosis of type 1 diabetes and using 670G pump for at least 1
324 month, and willing to have the 670G pump downloaded into a Carelink
325 Clinical research database.
- 326 2. The diagnosis of type 1 diabetes is based on the investigator's judgment; C-
327 peptide level and antibody determinations are not needed.
- 328 3. Age ≥18 years
- 329 4. Using Novolog or Fiasp® insulin at time of enrollment
- 330 5. Willing to use Fiasp® insulin
- 331 6. Total daily insulin dose is at least 0.3 units/kg/day

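### Part II plans no estimate of the trend across days of set wear (goal 4), and does not split its glucose outcomes by the overnight and daytime windows that goal 5e names

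*Combined protocol and SAP*

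**What the plan says.** Section 1.4 (Protocol Synopsis) lists the Part II goals. Goal 4 reads "Assess if Fiasp® becomes less effective over the life an infusion set (are sets", and its parenthesis goes on to ask about more frequent changing. Goal 5e reads "Does the performance of the 670G change overnight (MN to 6AM", then "and during the day (6AM to MN) in terms of time in range, mean" glucose and the percentage of readings under 70 mg/dL.

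Chapter 6 names one comparison for the Part II list. The early side is the "first two weeks of the study (before data was reviewed and changes made by the", and the sentence runs on "investigators) to data obtained during the last two weeks of the 3 month optimization" period. The method is a paired t-test, or a rank sum test for non-normal data. The items that matter here are:

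- a to c: time in range, percent time below 70 mg/dL and mean glucose, with no time-of-day window;
- g: "insulin delivery form MN to 6AM, and 6AM to MN", the only item split by those hours;
- j: the interval between set changes;
- l: "Average daily insulin, and mean glucose for each day of infusion set wear", with no contrast of its own;
- m: "Number of episodes of unexplained hyperglycemia in the first month vrs the" last month, which does state its own contrast.

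**The concern.** In both places the analysis answers a different question from the goal.

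Goal 4 is about what happens within a set as it ages. The named contrast is between two calendar windows. Applied to item l, it asks whether the wear-day profile changed between the start and the end of Part II. A null early-late result could then be taken as reassurance about set life, which it would not be. Section 1.3 says that the pump adjusts basal delivery by itself, so a loss of effect could appear in daily insulin, in glucose or in both. Both halves of item l are therefore needed.

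Goal 5e is about two parts of the day. A 24-hour value averages over them and can dilute or hide a change confined to one part.

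In both cases, leaving the estimate unspecified also leaves the choice of days, windows and summaries until after the data are seen.

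**Working it through.** The plan gives no power, precision or effect-size figure on this point, so there is nothing to reproduce. What follows is algebra, with illustrations under assumed values.

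**1. Early-late contrast on item l.** Let the mean on wear day k be m + b(k − 1) in the early window and m + d + b(k − 1) in the late window. Here b is the change per wear day and d is any overall shift between windows.

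- Early minus late on day k = −d. The trend b drops out, and with d = 0 the difference is 0 on every wear day.
- Day 3 minus day 1 within a set = 2b.
- With b = 5 mg/dL per day (assumed) and d = 0: early-late 0, within-set change 10 mg/dL. With b = 10: 0 and 20 mg/dL.
- If the trends differ (bE early, bL late), early minus late with d = 0 is (bE − bL)(k − 1). That is a change in the trend, not the trend.

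**2. Days used.** The two windows supply 2 × 14 = 28 days. If Part II lasts 6 weeks (Section 1.4; Chapter 2 says up to 6 weeks), that is 28 of 42 days. Chapter 6 also refers to a 3-month period, under which 28 days would be a smaller share. The documents conflict, so the number of usable days cannot yet be stated.

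**3. Why by-day means alone can mislead.** Chapter 3 (Part 2) has sets replaced after certain unexplained high glucose readings, so failing sets leave the later wear days. As an illustration, assume that 10% of sets run 60 mg/dL high on day 2 and are then replaced, and that the rest do not change. The 10% is borrowed from Section 1.2.1, where wear ended early in 10% of 210 Fiasp infusions and 4% of 98 aspart infusions, a non-significant difference. The documents do not attribute those events to lost effect.

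- Day 2 mean = 0.10 × 60 = +6. Day 3 mean over the remaining 90% = 0. The profile 0, +6, 0 looks like recovery although no set improved.
- Range: an excess of 30 mg/dL gives 0, +3, 0; 100 mg/dL gives 0, +10, 0; a 4% rate at 60 mg/dL gives 0, +2.4, 0.
- A fit with set fixed effects, per 100 sets, solves 65·b2 − 30·b3 = 300 and −30·b2 + 60·b3 = 0. This gives b2 = +6 on day 2 and b3 = +3 on day 3.
- A pooled within-set linear slope on the same data is 300/185 = 1.6 mg/dL per day.

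A within-set model lessens the distortion, by an amount that depends on its form, but does not remove it.

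**4. Goal 5e.** With readings spread evenly over the day, 24-hour change = (6/24) × overnight change + (18/24) × daytime change.

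- Overnight +8 points, daytime 0 (assumed): 8 × 0.25 = +2 points.
- Overnight +6, daytime −2 (assumed): 1.5 − 1.5 = 0.
- In general, an overnight change x shows as x/4 and is cancelled by a daytime change of −x × 6/18 = −x/3.

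**The case against.** The strongest reply is that goal 4 is not left unanswered. Its parenthesis offers a marker of lost effect, more frequent changing, and item j measures it. Item m adds counts of unexplained hyperglycemia, and item l supplies values by wear day from which a trend can be read. This stands. A reader might infer that goal 4 has no numerical answer at all, and the documents do not support that.

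A second reply is that item l may be meant as a comparison across wear days, since item m shows that items can carry their own contrast. That reading is possible, but item m states its contrast and item l does not. The zero in step 1 applies to the contrast that Chapter 6 names. On the other reading, the estimate and its interval are still unspecified.

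Third, goal 5e already names the outcomes and windows, so investigators who follow it would split the data anyway. This also stands: aligning the two lists is enough.

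Fourth, one might scale the effects to the Table 1 changes in Section 1.2.2. Those compare a Manual Mode run-in with three months of Auto Mode, whereas Part II subjects already use the 670G and Fiasp. They say nothing about the size of a change in Part II or its timing within the day, so they are not used here.

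Finally, Chapter 6 calls this an unpowered pilot. That limits how much weight any result can bear, but a stated goal still needs a matching summary.

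**Conclusion.** Both mismatches are in the text. For item l, the named contrast is 0 for any wear-day trend common to both windows, whatever its size, so it does not test whether effect falls over the life of a set. For items a to c, an overnight change counts for 6/24 of the 24-hour value and can be fully offset by a daytime change one third as large. The first result rests on applying the named contrast to item l, with an equal trend and no overall shift between windows. The second rests on evenly spread readings. The mg/dL and percentage-point examples are illustrations, not forecasts.

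A reader might also infer that a wear-day slope would show that Fiasp itself loses effect. Part II has no aspart arm, so a trend could equally be ordinary set ageing. Nor is the trial's validity at stake: these are exploratory outcomes from data that the study already collects. The change is worth making before analysis because it costs little.

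**What to change.** 1. **Item l.** Estimate the within-subject change across wear days in daily insulin and in mean glucose, with a 95% CI, using all Part II days. One suitable model has wear day as a fixed effect and sets nested in subject. Show the number of sets contributing at each wear day and the number replaced for unexplained hyperglycemia. Report this beside item j as exploratory evidence for goal 4. State that it cannot separate Fiasp from set ageing and that replaced sets still distort later days. Keep the early-late comparison as a secondary description.
2. **Items a to c.** Report each for 24 hours, midnight to 6 AM and 6 AM to midnight, with the early-late comparison in each.
3. **Length of Part II.** Reconcile the 6-week and 3-month statements before giving the number of usable days.

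The cost is a few more exploratory estimates from pump and sensor downloads already planned, with no new visits or subjects. They should be presented as estimates with intervals, not as claims of significance. Later wear days may be sparse: the background study in Section 1.2.3 had too few meals to analyse after day 4 of set life.
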